### **3.8 Minorities and Women**

No patients will be excluded on the basis of race, ethnicity, or sex. The clinical coordinating center will monitor recruitment of minorities and women. If necessary, additional recruitment efforts will be made to ensure that the aggregate patient sample contains representative race/ethnicity and sex subsets.

## **4. STUDY INTERVENTIONS**

### **4.1 Treatment of Study Participants**

A summary of the trial’s schedule of events is included in Appendix A.

Timing of study procedures is based on the time of randomization, which is defined as “Time 0”. The primary outcome will be assessed on Study Day 7, which corresponds to 7 days after randomization.

Study medications will be administered by clinical or research personnel while the patient is hospitalized. The study medication will be administered within 4 hours of randomization. On Study Day 1, study personnel will review patient records to confirm administration of the study drug and document the volume of magnesium citrate

and the probiotic Floranex was consumed. Research personnel will assess patients at Day 1-5, 7 and through Day 29; these assessments will be completed by phone if the patient has been discharged from the hospital.

## **4.2 Study Arms**

### **Magnesium Citrate plus The probiotic Floranex Arm:**

Participants assigned to the magnesium citrate plus the probiotic Floranex arm will receive 1 bottle of magnesium citrate 296 mL PO once to be taken within a 4-hour period, (about 10 oz.). Because magnesium citrate remains within the intestinal lumen, a second bottle can be provided if there is limited bowel movement. Patients will be asked to take 2 capsules of the probiotic Floranexs twice daily for six days or until discharge, whichever is earlier.

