#### **Exclusion Criteria**

- 1. Prisoner
- 2. Pregnancy
- 3. Breast feeding
- 4. Current infectious or noninfectious diarrheal illness
- 5. Unable to randomize within 21 days after onset of acute respiratory infection symptoms
- 6. Unable to randomize after hospital arrival
- 7. Colonic obstruction
- 8. Unresolved hypovolemia
- 9.  $\text{CrCl} < 30\text{ml/min}$
- 10. Hypermagnesemia
- 11. Diagnosis of Long QT syndrome
- 12. Known allergy to magnesium citrate or the probiotic Floranex
- 13. Unresolved electrolyte imbalance such as hypokalemia or hypocalcemia. The patient can be enrolled if electrolytes are corrected and sustained.
- 14. Receipt of  $> 1$  dose of magnesium citrate or any other colonic cleanser in the 7 days prior to enrollment
- 15. Inability to receive enteral medications
- 16. Refusal or inability to be contacted on Day 15 for clinical outcome assessment if discharged prior to Day 15
- 17. Concurrent medical illness that interferes with clinical assessmentPrevious enrollment in this trial
- 18. The treating clinical team does not believe equipoise exists regarding the use of magnesium citrate plus the probiotic Floranex for the treatment of this patient.
- 19. Participating in any other COVID-19 therapeutic trial

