### **Placebo Arm**

Participants randomized to the placebo arm will receive matching carbonated lemon water 296 mL PO once to be taken within a 4-hour period, (about 10 oz.) and 2 over-encapsulated microcrystalline pills capsules twice daily for six days or until discharge, whichever is earlier. The placebo will be flavored to match the taste of the interventional arm.

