## **4.6 Criteria for Stopping Study Drug**

Administration of the blinded study drug may be stopped temporarily or permanently for (a) adverse events, (b) results of on-study monitoring, (c) clinical deterioration, or (d) evidence of an alternative cause to the patient’s symptoms.

If a patient experiences an adverse event that the patient (or legally authorized representative), treating clinicians, or investigators feel merits temporarily or permanently stopping the study drug, the study drug will be stopped.

The explanation for stopping the study drug will be recorded in the case report form, and the adverse event will be recorded and reported according to the adverse event guidelines below. If the adverse event resolves to the extent that the patient (or legally authorized representative), treating clinicians, and investigators feel that resuming the

study drug is appropriate, the study drug will be resumed, and this information will be recorded in the case report form.

Patients on study may experience clinical deterioration due to their illness. Clinical deterioration will be defined as a decrease of 1 point or more on the ordinal scale for the primary outcome (e.g., patient transitions from “hospitalized on supplemental oxygen” to “hospitalized on non-invasive ventilation or high flow nasal cannula”). Patients who experience clinical deterioration in either group may be administered other antivirals or immunomodulators as “rescue therapy”. For patients who experience clinical deterioration for which treating clinicians feel optimal care would be to stop the study drug, unblind group assignment, and administer magnesium citrate and/or the probiotic Floranex to patients in the placebo group, the study drug will be stopped, the site investigator will contact the coordinating center to receive the unblinded study group assignment, and any additional treatment will be deferred to treating clinicians. In this situation, the following data will be recorded in the case report form: the criteria met for clinical deterioration; the reason for stopping study drug and unblinding; use of magnesium citrate, other antivirals, and immunomodulators; and study outcomes.

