## **6.2 Study Assessments/Procedures: Randomization to Hospital Discharge (Daily)**

- Study Variable Data Collection
  - Medication Assessment
  - Assess for clinical diagnosis of deep vein thrombosis (DVT) or pulmonary embolism (PE)
  - Oxygen/Ventilation assessment including S/F ratio, ventilation type, & vasopressor use (if applicable)
  - ARDS Assessment by Berlin Diagnostic Criteria (if applicable)
  - ICU admission/discharge information (if applicable)
  - Death date (if applicable)
  - Safety Outcomes: Dehydration, Seizure, Atrial or ventricular arrhythmia, Cardiac arrest, Symptomatic Hypotension, Acute kidney injury, Receipt of renal replacement therapy, Symptomatic hypoglycemia
  - Hospital discharge including patient destination at discharge

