#### **9.1.1 Potential risks of receiving magnesium citrate**

Common Side effects of magnesium citrate include:

Abdominal cramping

Diarrhea

Electrolyte imbalance

Gas (flatulence)

Nausea

Vomiting

Hypermagnesemia (high levels of magnesium in the blood).

Side effects that can occur with Hypermagnesemia:

Nervous system

- Muscle weakness, decrease in tendon reflexes, mental confusion, or sedation when serum magnesium (Mg) levels increase to 4 to 7 mEq/L,
- Slowed respiratory rate and hypotension when serum magnesium (Mg) levels increase to 5 to 10 mEq/L

- Profound mental depression, areflexia, coma and respiratory paralysis when serum Mg levels increase to 10 to 15 mEq/L
- Death possible when serum Mg levels rise to 15 mEq/L or higher.

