#### Gastrointestinal

- Nausea when serum Mg levels rise to 4 to 5 mEq/L.
- Rare cases of paralytic ileus associated with serum Mg levels greater than 5 mEq/L have been reported.
- 

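### Section 4.2 allows a second bottle of magnesium citrate on limited bowel movement alone, with no check against the entry exclusions, and describes it only for the active arm

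*Combined protocol and SAP*

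**What the plan says.** Section 4.2 (active arm) gives one bottle of magnesium citrate, 296 mL, over a 4-hour period, and then states: "Because magnesium citrate remains within the intestinal lumen, a second bottle can be provided if there is limited bowel movement". It gives no examination, laboratory result, interval or decision-maker. The placebo arm is to receive "matching carbonated lemon water 296 mL PO once to be taken within a 4-hour period", and no second bottle is mentioned there.

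The Section 3 exclusion list bars entry for colonic obstruction (item 7), unresolved hypovolemia (8), creatinine clearance below 30 mL/min (9), hypermagnesemia (10) and unresolved electrolyte imbalance (13). Item 13 adds: "The patient can be enrolled if electrolytes are corrected and sustained". Section 3.3 says that these criteria exist mainly for safety.

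Section 9.1.1 has a list introduced by "Common Side effects of magnesium citrate include", which contains both electrolyte imbalance and hypermagnesemia. Its gastrointestinal part adds: "Rare cases of paralytic ileus associated with serum Mg levels greater than 5 mEq/L have been reported".

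On monitoring, Section 6.2 lists daily items beginning "Safety Outcomes: Dehydration, Seizure, Atrial or ventricular arrhythmia, Cardiac arrest, Symptomatic Hypotension, Acute kidney injury". Section 4.6 says: "Administration of the blinded study drug may be stopped temporarily or permanently for (a) adverse events, (b) results of on-study monitoring".

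**The concern.** The protocol treats certain states as making magnesium citrate unsafe to start. It then allows a repeat dose without asking whether any of them has since appeared, although two are side effects it lists for the drug itself. Followed as written, the rule can give a second bottle to someone who would no longer qualify for the first.

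The trigger is also ambiguous. Little bowel movement after a cathartic may mean that the dose was too small, or that the bowel is obstructed or not moving. Only the first reading supports repeating the dose. The stated reason, that the drug stays in the gut lumen, does not address obstruction, ileus or volume loss.

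There is a blinding side as well. Staff judging the trigger do not know the assignment. If a request can be met in one arm and not in the other, the response can reveal the arm.

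**Working it through.** The plan gives no figure for this point, so the check is mainly a comparison of its sections.

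**Step 1. Entry exclusions against what happens before bottle 2** (Section 3 item numbers)

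| Exclusion | Can it change or be missed after bottle 1? | Post-dose item named in 6.2 or Appendix A | Condition for bottle 2? |
|---|---|---|---|
| 7 Obstruction | Nothing says bottle 1 causes it, but the trigger can be its sign | None | No |
| 8 Hypovolemia | Yes; dehydration is a safety outcome in 5.3 | Dehydration, daily | No |
| 9 CrCl below 30 | Little scope within hours | Acute kidney injury, daily | No |
| 10 Hypermagnesemia | Yes; listed as common in 9.1.1 | None | No |
| 13 Electrolyte imbalance | Yes; listed as common in 9.1.1, and entry is open after correction | None | No |

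Two of the five have a daily recorded counterpart, three have none, and none is a condition for the second bottle. Choosing these five is a judgement. Items 10, 13 and 8 carry most of the weight, item 7 matters because of the trigger, and item 9 adds least.

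**Step 2. Is a check required elsewhere?**

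- Section 4.5 relies on routine inpatient care plus a daily review aimed at drug interactions.
- Section 4.6 covers stopping the study drug. It makes no result a precondition for giving more.
- Section 11, item 3, refers to preventive monitoring in general terms, with medications and EKG as examples.
- Section 11.2 has investigators look for adverse events each day to Day 7 or discharge.
- Appendix A marks eligibility assessment before enrollment only. It has no magnesium, electrolyte or creatinine row. Its blood-sample row (Days 1 and 7) matches the T-cell collections in Sections 6.1 and 6.2.1.3.

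None of these makes the second bottle conditional on anything.

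**Step 3. Size**

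- Volume with a second bottle: 2 × 296 = 592 mL.
- Active-arm participants: 30 / 2 = 15 (Section 7.1 plans 15 per arm).
- The share meeting the trigger is not given. Assuming 10% to 50%: 0.10 × 15 = 1.5 to 0.50 × 15 = 7.5, or about 2 to 8 people. The possible limits are 0 and 15.

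**Step 4. The two arms**

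The active-arm text provides one bottle and a possible second. The placebo text provides one. Sections 2.3 and 3.7 blind participants, clinicians and study staff, with the pharmacy supplying the allocated pack. As written, a second bottle exists in one arm only.

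**The case against.** The strongest reply is that this is a discretionary dose in monitored inpatients. Section 4.6 does more than permit stopping: if the patient, the treating clinicians or the investigators judge that an adverse event warrants it, the drug is stopped. Section 11.2 requires a daily look for adverse events, and dehydration and kidney injury are followed daily. If the repeat is given on Day 1, as the drug-delivery mark in Appendix A suggests, re-testing renal function so soon would yield little. Section 4.1 has staff document the volume consumed, so the maximum possible exposure is known even without the assignment. The link from limited bowel movement to obstruction or ileus is clinical inference. The protocol does not draw it, and it calls ileus rare.

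All of this stands as a limit on the size of the point. None of it supplies a check before the second bottle, because these provisions respond to events or are general.

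Four stronger readings are tempting and are not supported:

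- **That nobody looks for these states.** Sections 6.2 and 11.2 show otherwise for dehydration, kidney injury and adverse events generally.
- **That serious toxicity is likely.** No event rate is given, creatinine clearance below 30 is excluded in Section 3, and the protocol says most of the drug stays in the lumen.
- **That the first bottle usually causes hypermagnesemia.** One sentence in Section 9.1 calls a mild rise typical, but the reason it gives points the other way. The word is probably a slip, and nothing here depends on it.
- **That dosing is open-ended.** The text allows one further bottle, two in total. Only the interval is unstated.

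**Conclusion.** The point holds in a limited form. Section 4.2 permits a doubling of the magnesium citrate dose on one ambiguous sign. It does not require confirmation that the participant is still free of hypermagnesemia, electrolyte imbalance, hypovolemia or obstruction. It also describes the extra bottle for one arm only, which works against the blinding.

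This is a real gap in a dosing rule, since following the rule exactly can dose someone the entry criteria would exclude. It remains a cheap improvement to safety and blinding. The documents do not show expected harm or an effect on the primary comparison. The size, about 2 to 8 of 15 active participants, rests wholly on the assumed 10% to 50% usage. Confidence is high that the text contains no such check, and moderate on how much it would matter in practice, because a careful clinician may well check anyway.

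**What to change.** In Section 4.2, state that one additional bottle of the assigned blinded study drink may be given, in either arm, within a stated window (for example 24 hours), only after a clinician confirms both of the following:

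- at the bedside, no sign of obstruction, ileus or hypovolemia;
- on the most recent inpatient creatinine, electrolytes and any available magnesium, none of exclusions 9, 10 or 13 is present.

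Have pharmacy supply a matching second placebo bottle, and align the drug-delivery row of Appendix A with the window. Withhold no result from treating clinicians, since Section 4.5 relies on their routine monitoring. Do not create a dose-release role for the Medical Monitor, whose task in Appendix C is assessing events.

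The simpler alternative is to delete the second-bottle option, so that both arms receive one bottle, once. That needs no checks.

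**Cost.** One or two sentences and a small schedule change. Assume 10% to 50% of 15 active participants (1.5 to 7.5) and 50% to 100% of 15 placebo participants (7.5 to 15) meet the trigger. The total is then 1.5 + 7.5 = 9 to 7.5 + 15 = 22.5 brief checks, with a maximum of 30. Many could probably use results already in the chart, in line with the emphasis in Section 6 on health-record data. The downsides are an occasional added blood test, some patient contact in the placebo arm, and a visible magnesium value that might hint at assignment.

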## **2.3 Study Design**

We will conduct an investigator-initiated, single center, blinded, placebo-controlled, randomized clinical trial evaluating magnesium citrate plus the probiotic Floranex for the treatment of adults hospitalized with COVID-19. Patients, treating clinicians, and study personnel will all be blinded to study group assignment.

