### **3.7 Randomization and Blinding**

Participants confirmed to meet all eligibility criteria who have provided informed consent will be randomized 1:1 to magnesium citrate plus a the probiotic Floranex versus placebo. A randomization code will be provided to the site investigator or delegate from a centralized, web-based platform. Randomization will require provision of the screening number and confirmation of patient eligibility.

Randomization will be completed in permuted blocks of varying size and stratified by site. The randomized sequence allocation will be stored on a secure server and will not be available to site study personnel. Site research personnel will have a unique Personal Identification Number (PIN) to access the randomization system. Each subject will receive a computer-generated randomization ID number. The computer-generated randomization ID number will be provided to the pharmacy who will provide a dose pack containing magnesium citrate plus a the probiotic Floranex or placebo. The participant, treating clinicians, study personnel, and outcome assessors will all remain blinded to group assignment until after the database is locked and blinded analysis is completed.

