## **4.4 Co-Interventions**

This trial will control the use of magnesium citrate plus the probiotic Floranex vs placebo during the intervention period. Enrolled participants will not receive open-label magnesium citrate or the probiotic Floranex during the intervention period. All other treatment decisions will be made by treating clinicians without influence from the protocol. Administration of other antiviral medications (“rescue therapy”) will be allowed. The decision to administer other antiviral medications will be made by treating clinicians and will be recorded in the case report form. The decision to administer immunomodulating medications, including corticosteroids, will be made by treating clinicians and will be recorded in the case report from.

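### The second bottle is allowed in the active arm only, with no matching placebo bottle, so each use as written risks revealing that patient's allocation to blinded staff.

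*Combined protocol and SAP*

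**What the plan says.** Section 4.2 describes the two arms separately. Active patients take one 296 mL bottle of magnesium citrate. The text then adds, giving a reason specific to that drug (it stays in the bowel lumen), that "a second bottle can be provided if there is limited bowel movement". Placebo patients receive "matching carbonated lemon water 296 mL PO once to be taken within a 4-hour period", with the same capsule schedule and a matched flavor. No second bottle is mentioned for them.

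On blinding, section 2.3 states: "Patients, treating clinicians, and study personnel will all be blinded to study group assignment". Section 3.7 adds outcome assessors and a time limit: "The participant, treating clinicians, study personnel, and outcome assessors will all remain blinded to group assignment until after the database is locked". On supply, section 3.7 says that the randomization ID "will be provided to the pharmacy who will provide a dose pack". Section 4.1 has clinical or research staff give the study drug, and on Day 1 "study personnel will review patient records to confirm administration of the study drug and document the volume of magnesium citrate" and of Floranex consumed.

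Section 4.4 says "Enrolled participants will not receive open-label magnesium citrate or the probiotic Floranex during the intervention period". It also says "All other treatment decisions will be made by treating clinicians without influence from the protocol". The exception to the open-label bar is section 4.6, where a patient who deteriorates may be unblinded through the coordinating center, with the reason recorded.

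**The concern.** Those who observe a poor bowel response and would ask for the second bottle are blinded staff. An instruction that exists for one arm only cannot be followed by someone who does not know the arm. If someone who does know the arm answers the request according to the text, the answer itself discloses the allocation.

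This matters because the primary outcome is open to influence by people who know or guess the arm. Under section 4.4, treating clinicians decide on antivirals, corticosteroids and all other care. In Appendix E, scores 4 to 6 depend on whether the patient is in hospital and on the type of oxygen support. Patients discharged before Day 7 are scored by telephone interview (section 6.3.1), so the patient's own blinding counts too. The protocol does not say when a second bottle may be given, but Appendix A lists study drug delivery on Day 1 only, so use would be expected before the Day 7 score.

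**Working it through.** The plan has no figure of its own to reproduce here. The check compares the texts and then applies Bayes' rule to show what a second bottle would reveal.

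**Step 1. Compare the arms (section 4.2).**

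| Element | Active | Placebo |
|---|---|---|
| Volume | 296 mL, once | 296 mL, once |
| Time to drink | 4 hours | 4 hours |
| Capsules | 2 twice daily, six days or until discharge | Same |
| Second bottle | Allowed on poor bowel response | Not mentioned |

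**Step 2. Look for the missing provision elsewhere.** Randomization (sections 1.0 and 3.7), treatment (4.1), co-interventions (4.4), stopping and unblinding (4.6) and the schedule (Appendix A) contain no placebo second bottle and no route for requesting one. Because of the open-label bar in section 4.4, a second bottle for a placebo patient would have to be placebo, and the placebo text does not provide it.

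**Step 3. What a supplied bottle reveals.** Let *a* and *p* be the shares of active and placebo patients given a second bottle. With 1:1 allocation,

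P(active | second bottle) = a / (a + p).

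As written p = 0, so the result is a / a = 1.00 for any a > 0, against 0.50 beforehand. This does not depend on how often the bottle is used.

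**Step 4. Separate the bottle from the bowel response.** The protocol gives no rates. Assume, for illustration only, that a poor bowel response occurs in 10–30% of active and 50–90% of placebo patients. The response alone then gives P(active) between 0.10 / (0.10 + 0.90) = 0.10 and 0.30 / (0.30 + 0.50) = 0.375.

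- As written, supplying the bottle moves this to 1.00.
- If every active request were granted, declining would move it to 0. If only a share *s* of active requests were granted, declining gives a(1 − s) / [a(1 − s) + p], where *a* and *p* are now the shares with a poor response. This is below a / (a + p) for any s > 0.
- With a matched bottle for any patient who meets the trigger, the answer to the request adds nothing. The probability stays at 0.10 to 0.375, and all of that information comes from the bowel response.

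**Step 5. How many patients.** Section 7.1 plans 30 patients, 15 per arm.

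- Each use: 1/30 = 3.3% of the trial.
- Assumed 1, 3 or 6 uses: 1/30 = 3.3%, 3/30 = 10%, 6/30 = 20%.
- At the assumed 10–30% of active patients: 0.10 × 15 = 1.5 to 0.30 × 15 = 4.5 patients identified by a supplied bottle.

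These counts leave out declined requests.

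**The case against.** The strongest reply is that the asymmetry is only a drafting habit. Supply is coded and dispensed by pharmacy, and blinded staff could not operate an active-only rule, so a second bottle from the same coded supply for anyone may be what was meant. The protocol does use the active drug's name for procedures that must cover everyone, such as the consumption record in section 4.1 and the interaction screening in section 4.5. Nor does the word once in the placebo text exclude a second bottle, since the active text also says once before allowing another. This reading is plausible, but it is not written down. A pharmacist following section 4.2 literally would supply second bottles to active patients only.

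Several further points limit the size of the problem, and they stand:

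- The rule is permissive and its trigger is undefined, so a declined request suggests placebo without proving it.
- The signal reaches only people who know the arm-specific text, and the protocol does not show that patients or treating clinicians would.
- Section 9.1.1 lists diarrhea and cramping as common effects of magnesium citrate. Bowel response is therefore a cue in potentially every patient, and no wording will remove it.
- The frequency is unknown, and no effect on the Day 7 score has been demonstrated.

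The laxative cue does not justify the second one. It is probabilistic and comes with the drug, whereas the supplied bottle is conclusive as written and avoidable.

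**Conclusion.** The concern holds. The plan contains a dosing rule specific to one arm that blinded staff cannot apply, and following its text would identify each active patient who receives a second bottle. That conclusion needs only the 1:1 allocation and the absence of a placebo bottle. The number of patients affected is unknown, and every count above rests on assumed rates. The path from knowing the arm to a changed Day 7 score is credible but not quantified.

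This should be corrected, but it does not by itself invalidate the trial. Confidence is moderate, because a coded second bottle for both arms may have been intended.

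**What to change.** Either put the same second-bottle sentence in both arm descriptions or delete it from both. The choice is a clinical one for the sponsor. Deletion removes the visible event altogether.

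If the provision is kept:

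- Define one trigger and a time window, applied to every patient.
- Let blinded staff make the request without reference to arm.
- Have pharmacy dispense matching active or placebo stock under the randomization ID, so that every valid request is met.
- Record any second bottle and the volume taken in both arms. The Day 1 record in section 4.1 should refer to study drug, since it now names only magnesium citrate and Floranex as the products whose volume is documented.

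The cost is protocol wording and extra placebo bottles. At the assumed 50–90% trigger rate on placebo, 0.50 × 15 = 7.5 to 0.90 × 15 = 13.5, or about 8 to 14 bottles, with a ceiling of 15 at one per placebo patient. Those patients would drink 2 × 296 = 592 mL of lemon water in total. Sample size and analysis are unchanged. The bowel response will remain a partial cue to allocation.
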